CLINICAL TRIAL DOCUMENT COVER PAGE

Official Title of the Study:

Adherence to the Mediterranean Diet Following Nutritional Education and Its Effect on Anxiety, Depression, Fatigue, and Sleep Quality Among a Group of Lactating Women in Jordan: An Interventional Study

NCT Number: Not yet assigned

Document Type: Protocol / Statistical Analysis Plan

Version Number: Version 1.0

Document Date: May 2026

Sponsor / Institution: Applied Science Private University

Principal Investigator: [name]

Contact Information: [contact]

Title of the project

Adherence to the Mediterranean Diet Following Nutritional Education and Its Effect on Anxiety, Depression, Fatigue, and Sleep Quality Among a Group of Lactating Women in Jordan: An Interventional Study.

The outcome:

The aim of our study is to compare the degree of adherence to MedDiet between women who received educational and nutritional interventions during 6 months of follow-up and those without such interventions, and to examine the impact of these interventions on mothers' nutritional status, anthropometrics, and mental health.

The objectives:

The objectives of the current study are:

1. Investigate the impact of an educational intervention on MedDiet among a group of lactating women aged 18-40 years and above in Jordan over a six-month follow-up period.
2. Investigate the relationship between MedDiet adherence, obesity, and mental health. among a group of lactating women aged 18-40 years and above in Jordan over a six-month follow-up period.

Protocol**Study design and setting**

An intervention study is conducted for lactating mothers with follow-up at 3 and 6 months. Participant recruitment focuses on lactating women with infants aged 1-2 months.

The study is conducted at the Ministry of Health's childbirth vaccination clinics in Amman and Irbid, Jordan. The clinics have a fine reputation for maternal and child health services with organized working and research systems.

Ethical considerations

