Ethical approval was obtained from the Ministry of Health (MOH/REC/2024/502) and the IRB at Philadelphia University (1/1/2024-2025). The research complies with the ethical principles for medical research involving human subjects of the Helsinki Declaration. (“World Medical Association Declaration of Helsinki: Ethical Principles for Medical Research Involving Human Subjects,” 2014). All participants provide written informed consent before starting, and their right to privacy, anonymity, voluntary participation, and confidentiality are observed.

Participants

Participants consisted of eligible lactating women aged 18–40. The exclusion criteria are (1) all women aged below 18 or above 40, (2) lactating women diagnosed with mental diseases, and (3) women who were already on supplementation for managing deficiencies such as iron, B12, and vitamin D or hormonal disturbances, mainly thyroxine.

Sample size:

The sample size is calculated using 95 % confidence and an RR of 1.9, considering a 20 % non-response rate in cohorts (Rahman et al., 2007), which assumes the number of participants to be 180 based on the population of all eligible candidates who are sequentially enrolled in the study for 6 months, with an expected total research duration of 8 months.

Instruments

Validated Arabic public-domain questionnaires are distributed to collect demographic data, including age, weight, pre-pregnancy BMI, nationality, income, education, employment, insurance status, marital status, gestational age, number of children, and smoking status. Also, anthropometry and possible confounders such as physical and psychological abuse. All participants are interviewed face-to-face, and trained nutrition researchers fill out questionnaires.

A. Questionnaires:

Validated Arabic version of:

- **MEDAS:** A 14-item Mediterranean Diet Adherence Screener (14-MEDAS) is used to assess the adherence of eligible participants to MedDiet
- **Food Frequency questionnaire:** The questionnaire assesses habitual dietary intake by questioning the frequency with which food items are consumed over one week. It is adjusted in a cultural context; foods not typically used in the Jordanian diet are omitted, while foods typically used are added (Tayyem et al., 2014).

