Descriptive statistics and correlations for all quantitative and categorical study variables are calculated at baseline and at the end of the study to present the prevalence of depression, anxiety, and stress severity. Appropriate descriptive statistics such as percentages, means, and standard deviation summarize the data depending on the variable type. The Shapiro–Wilk test will be applied to assess data normality. Data are described using means (SD) and percentages. The student's t-test will be used to compare the means and medians of independent variables between groups; Pearson's Chi-Square test will be used for categorical data to test for association and probability, especially the relationship between sociodemographic variables, nutritional status, and the severity of depression, anxiety, and stress. Moreover, the significance level was set at $p < 0.05$, along with logistic regression, to identify the determinants of the severity of depression, anxiety, and stress among pregnant women attending the clinics. For the ordinal regression modeling, the severity is coded as normal = 0, mild = 1, moderate = 2, and severe = 3. The multivariable ordinal logistic regression model includes Variables statistically significant at $P \leq 0.05$ in the bivariate analyses.

References:

- Arnarson, P. Ö., Ólason, D. P., Smári, J., & Sigurdsson, J. F. (2008). The Beck Depression Inventory Second Edition (BDI-II): Psychometric properties in Icelandic student and patient populations. *Nordic Journal of Psychiatry*, 62(5), 360–365. <https://doi.org/10.1080/08039480801962681>

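### Pearson's chi-square, the test named for nutritional status against severity, ignores the order of severity and of any exposure classes; used as the model-entry screen, it loses power materially

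*Combined protocol and SAP*

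**What the plan says.** Under The objectives, the second objective is to "Investigate the relationship between MedDiet adherence, obesity, and mental health" over six months. Under Instruments and Questionnaires, the trial collects age, weight, pre-pregnancy BMI, anthropometry, food-frequency intake and a diet quality index of 14 healthy and 7 unhealthy components. For adherence, "A 14-item Mediterranean Diet Adherence Screener (14-MEDAS) is used to assess the adherence of eligible participants to MedDiet". All of these can be held as numbers.

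Under Statistical analysis, Pearson's chi-square "will be used for categorical data to test for association and probability, especially the relationship between sociodemographic variables, nutritional status" and severity. Severity is coded 0 (normal) to 3 (severe) for an ordinal regression. Entry to that regression follows a significance rule: "The multivariable ordinal logistic regression model includes Variables statistically significant at $P \leq 0.05$ in the bivariate analyses".

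The section also lists correlations for all quantitative and categorical variables, described as presenting the prevalence of severity, and a t-test between groups. It does not define nutritional status, give classes or cut-points, or say which bivariate analysis drives the entry rule.

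**The concern.** The one test named for nutritional status against severity treats both sides as unordered. It discards the severity ordering on which the plan's own regression depends, and the ordering of any BMI or diet classes. A graded relation, which is the natural form for adherence or obesity against symptoms, is then tested on several degrees of freedom when one would do.

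The screen makes this more than a loss in a side table. A variable that misses P <= 0.05 is kept out of the multivariable model and may be reported as not a determinant. If the measured scores are cut first, the result also depends on where the cuts fall.

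**Working it through.** **Inputs from the plan.** Significance level 0.05; four ordered severity levels; 180 women; 20% non-response. If 180 already includes the non-response, 180 x 0.8 = 144 are analysed. Both 144 and 180 are used below.

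**The plan's own figure.** The 180 cannot be reproduced, because the Sample size section gives 95% confidence and a relative risk of 1.9 but no power or baseline risk. Assuming 80% power and the usual two-proportion formula without continuity correction, it fits a baseline risk of about 25% for two equal groups (71 per group, 142 in total, 142/0.8 = 178) or about 31.5% for three equal groups (180). No power is stated for the chi-square or ordinal analysis, so there is nothing to compare with directly.

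**Assumptions, none of them in the documents.** Exposure and symptoms are bivariate normal with latent correlation r from 0.10 to 0.30. Symptoms are cut into four severity levels. The exposure is left uncut or cut into two, three or four classes.

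**Method.** For chi-square on a table with k exposure classes and four severity levels, df = 3(k - 1). The non-centrality is n x sum of (p_ij - p_i p_j)^2 / (p_i p_j), and power is the chance that the non-central chi-square exceeds its 5% critical value. The comparators are 1-df tests that respect order: a trend test on the same classes, and an ordinal or rank test with the exposure uncut.

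**Example 1.** n = 144, r = 0.20, severity 50/20/20/10%, exposure in thirds.
- Chi-square: df = 6, critical value 12.59. The sum is 0.0253, so the non-centrality is 144 x 0.0253 = 3.64 and power is 24.6%.
- Trend test on the same classes: power 47.2%. On 1 df that corresponds to a non-centrality of about (1.96 - 0.07)^2 = 3.57.
- Uncut exposure, ordinal test: power 56.1%.

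The trend component (3.57) is nearly all of the 3.64, so the other five degrees of freedom mainly raise the critical value. The total loss is 56.1 - 24.6 = 31.5 points. Ignoring order accounts for 47.2 - 24.6 = 22.6 and the cut for 56.1 - 47.2 = 8.9.

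**Example 2.** n = 144, r = 0.25, severity 60/15/15/10%, by simulation.

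| Exposure classes | Chi-square | Order-respecting test, same classes | Uncut exposure |
|---|---|---|---|
| Two (80/20) | 37% | 46% | 70-72% |
| Three (45/35/20) | 39% | 64-65% | 70-72% |
| Four (5/40/35/20) | 28% | 64-65% | 70-72% |

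With three or four classes, respecting order recovers most of the loss. With two classes it recovers 46 - 37 = 9 points, and the cut itself costs about 71 - 46 = 25.

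**Range.** n = 144 or 180, severity 60/15/15/10% or 40/20/25/15%, the class splits of Example 2.

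| r | Loss, chi-square against uncut exposure |
|---|---|
| 0.20 to 0.30 | about 24 to 45 points |
| 0.15 | about 15 to 28 points |
| 0.10 | about 6 to 14 points |

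At r = 0.20 to 0.30 the cut alone costs about 4 to 10 points with three or four classes and about 20 to 28 with the 80/20 split. Simulated type I error was close to 5% for all tests, so the differences are not due to miscalibration.

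**The case against.** The strongest reply is that the plan limits chi-square to categorical data and never says that BMI or diet scores will be categorised. It lists correlations for all quantitative variables, and the entry rule speaks of bivariate analyses in the plural. An analyst could screen numeric scores by correlation, and the ordinal model accepts continuous covariates. This stands, and it makes the loss conditional. It does not remove the point. The listed correlations are described only as presenting prevalence, a two-sample t-test cannot compare a score across four severity levels, and chi-square is the only test tied by name to this relationship. If analysts may choose between a correlation and a chi-square at the screen, entry to the model is not prespecified.

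A reader might also infer that nutritional status is the exposure of objective 2. The documents do not support that: objective 2 names MedDiet adherence and obesity, and the aim lists nutritional status separately from anthropometrics, as something the intervention may change. Nor do they show that the scores must be cut.

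A further fair objection is that a significance screen can drop an objective 2 exposure whichever test feeds it. That is correct, so changing the test alone is not enough.

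**Conclusion.** The point holds as a weakness in a named method combined with missing definitions. Chi-square ignores an ordering that the plan itself codes, and an order-respecting alternative is already in the plan. If chi-square on classes is used as named, the loss is material at modest correlations and smaller at weak ones. The figures rest on assumed correlations, severity splits, class proportions and a bivariate-normal model; the documents supply none of these.

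It would be tempting to attribute the loss mainly to categorising BMI. That holds only for an obese yes/no split; with three or four classes the unordered test does most of the harm. The change should be made, but it does not bear on the comparison between the three intervention groups.

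**What to change.** In the Statistical analysis section:

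- Restrict Pearson's chi-square to truly nominal variables, such as nationality, marital status and insurance.
- Define nutritional status and state which bivariate test supplies the entry P value.
- Test BMI and anthropometry, MEDAS score, diet quality index, food intakes and age against severity on their measured scale. Use a continuous term in the ordinal logistic model already planned, with a non-linear term for BMI if needed, or a Spearman correlation.
- Use a 1-df trend test for ordered variables such as education and income.
- Keep BMI and adherence classes for descriptive tables only.
- Enter MEDAS score and BMI, the objective 2 exposures, in the multivariable ordinal model regardless of the screen.

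The cost is a few sentences of wording; no new data are needed. The small downside is that results are reported per unit, not as obese versus non-obese, and a U-shaped BMI relation would need the non-linear term.

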- **A diet quality questionnaire,** the food-based diet quality index, was created by synthesizing current nutrition knowledge. The questionnaire includes 14 "healthy" and 7 "unhealthy" food components known to affect health and prevent major diet-related diseases (Kronsteiner-Gicevic et al., 2021).
- **Depression, Anxiety, and Stress Scale-21 Items (DASS-21)** is a set of three self-report scales developed to measure the emotional states of depression, anxiety, and stress that can effectively assess mental health symptoms for individuals (Bryson et al., 2021; Effati-Daryani et al., 2020; Khouj et al., 2022).
- **Modified Fatigue Impact Scale (MFIS):** The MFIS is a modified version of the FIS that measures physical, cognitive, and psychosocial fatigue. Participants rate the impact of fatigue on their lives over the past 4 weeks on a scale of 0 (no problem) to 4 (extreme problem) (Strober et al., 2020).
- **The Pittsburgh Sleep Quality Index (PSQI)** measures general sleep quality and is a recommended questionnaire for studying global sleep and insomnia symptoms (Zitser et al., 2022).
- **The Beck Depression Inventory (BDII):** This depression self-report measure has been extensively researched and used in clinical and non-clinical populations. It has strong psychometric properties and is widely implemented in depression-related research (Arnarson et al., 2008).
- **SF-36 ARABIC**

B. Educational Intervention:

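### The statistics section names no by-arm analysis of diet adherence, fatigue or sleep and no primary outcome: it offers one generic two-sample t-test for a three-group trial, and its regression refers to pregnant women

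*Combined protocol and SAP*

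**What the plan says.** **Aim and outcomes.** Under the heading The outcome, the plan sets out to "compare the degree of adherence to MedDiet between women who received educational and nutritional interventions during 6 months of follow-up" and women without such interventions. It then adds impact on nutritional status, anthropometrics and mental health. The title adds "Its Effect on Anxiety, Depression, Fatigue, and Sleep Quality Among a Group of Lactating Women in Jordan". Objective 2 is observational: the relationship between adherence, obesity and mental health.

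**Population and design.** Study design and setting states: "Participant recruitment focuses on lactating women with infants aged 1-2 months", with follow-up at 3 and 6 months. Educational Intervention defines three groups: education with brochure and reminders, brochure only, and control.

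**Instruments.** The 14-item MEDAS "is used to assess the adherence of eligible participants to MedDiet". For fatigue, "The MFIS is a modified version of the FIS that measures physical, cognitive, and psychosocial fatigue". For sleep, the PSQI "measures general sleep quality and is a recommended questionnaire for studying global sleep and insomnia symptoms". DASS-21, a Beck depression inventory, a diet quality index, a food frequency questionnaire and the SF-36 are also listed.

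**Statistical analysis.** The section gives:
- descriptive statistics and correlations at baseline and end of study;
- a Student's t-test of the means and medians of independent variables between groups;
- chi-square tests, chiefly of sociodemographic variables and nutritional status against severity of depression, anxiety and stress;
- logistic regression "to identify the determinants of the severity of depression, anxiety, and stress among pregnant women attending the clinics", with an ordinal model whose terms are the variables significant at P ≤ 0.05 in bivariate analyses.

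The significance level is p<0.05. No outcome is called primary.

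**The concern.** The analysis section and the aim do not meet. Adherence comes first in the aim, and fatigue and sleep are in the title, yet the section names none of them, nor MEDAS, MFIS or PSQI. It does not mention intervention, control or arm. The one outcome it names is severity of depression, anxiety and stress.

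Two analysts could both follow this text and report different scales, pairs of arms and visits. With many scales, three possible pairs, two follow-up visits and no multiplicity rule, a chance finding somewhere becomes likely, and a reader could not tell which result had been planned. More data would not repair that afterwards.

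**Working it through.** **1. What the section specifies for each part of the aim**

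| Part of the aim or title | Named in Statistical analysis? | By-arm test, contrast and visit given? |
|---|---|---|
| Adherence (MEDAS) | No | No |
| Fatigue (MFIS) | No | No |
| Sleep (PSQI) | No | No |
| Depression, anxiety | Yes, as severity | No; arm is not a fixed term |
| Nutritional status | Yes, as a variable related to severity | No |
| Anthropometrics | No | No |

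The sample size paragraph cannot supply the missing primary outcome. It gives a relative risk of 1.9 without saying what it is the risk of.

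**2. The t-test sentence.** It refers to independent variables rather than outcomes and does not say that the groups are the arms. A t-test compares two means: it does not compare medians, and for three groups it leaves open which pairs are meant. No visit or baseline adjustment is stated.

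**3. False-positive risk**

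From the documents: three groups, alpha 0.05, no adjustment stated, total N 180. Assumptions: equal split (180/3 = 60 per arm), one visit, all three pairs t-tested, and one common correlation between scores, shown from 0 to 0.5. The tests are taken as two-sided, since the plan does not say.

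Number of scores:
- Five: MEDAS plus the title's four outcomes.
- Ten: MEDAS 1 + diet quality 1 + DASS-21 3 + MFIS subscales 3 + PSQI 1 + Beck 1 = 10, before the food frequency questionnaire, SF-36 and anthropometry.

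One score, three pairs: simulation gives about 0.12. The independence formula, 1 − 0.95³ = 0.143, is too high because the pairs share arms.

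Uncorrelated scores, three pairs, with 0.122 per score:
- five scores: 1 − (1 − 0.122)^5 = 0.48
- ten scores: 1 − (1 − 0.122)^10 = 0.73

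Uncorrelated scores, one pair, ten scores: 1 − 0.95^10 = 0.40.

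Correlated scores, by simulation with no true effects. Chance of at least one p<0.05:

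| Scores | Pairs | Correlation 0.5 | 0.3 | 0 |
|---|---|---|---|---|
| 5 | 3 | about 39% | about 44% | about 48% |
| 10 | 3 | about 55% | about 66% | about 73% |
| 10 | 1 | about 29% | about 35% | about 40% |

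Repeat simulations differ by about one percentage point. Using 48 per arm (60 × 0.8, for the plan's 20% non-response) leaves the figures essentially unchanged. Testing the 3-month visit as well would raise them.

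**4. What one named contrast keeps.** The standardised difference detectable with 80% power (power assumed; the plan states none) is (z for alpha + 0.84) × √(2/n):
- one contrast at 0.05: 2.80 × √(2/60) = 0.51 SD, or 2.80 × √(2/48) = 0.57 SD
- Bonferroni over three pairs: 0.59 SD or 0.66 SD

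**The case against.** The strongest reply is that a between-group test is stated, and that Educational Intervention uses the word groups for the three arms. A sympathetic reader can therefore apply the t-test to MEDAS, MFIS and PSQI scores by arm. That is a fair reading, so it would go too far to infer that the aim has no stated analysis at all. What the sentence does not supply is the outcome, the contrast, the visit or the error control.

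Three other strong inferences also fail:
- **That the regression is off-aim.** Objective 2 asks about adherence, obesity and mental health, and depression and anxiety are two of the title's four outcomes. The regression is partly on-aim; it just does not estimate the intervention effect.
- **That arm is excluded from the ordinal model.** The screen does not exclude it. Arm is simply not guaranteed a place.
- **That the wrong population will be analysed.** Enrolment of lactating women is unambiguous. The term pregnant women is a wording error that one word corrects.

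It is also fair to say that the error rates are conditional. The plan states no correlations, does not say that every pair will be tested, and does not say that MFIS subscales will be tested separately. The five-score row avoids the subscale count and still gives 39-48% with three pairs.

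**Conclusion.** The point stands in this form: the plan contains only a generic two-sample test between unspecified groups, names no by-arm analysis of adherence, fatigue or sleep, does not fix arm in the ordinal model, designates no primary outcome and controls no multiplicity. The missing primary outcome and by-arm analysis are the material defects; the population term is minor. Unadjusted testing would carry a false-positive chance well above 5% under every scenario examined, from about 12% for a single score over three pairs to 55-73% for ten. Those sizes rest on the assumed equal split, correlations and set of tests. The defect itself rests on the text alone. It should be fixed before analysis.

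**What to change.** Before any by-arm data are examined, put the intervention analysis first in the section:

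1. **Primary.** MEDAS score at 6 months, education plus brochure versus control, two-sided 0.05, from a linear model (ANCOVA) with three-level arm and baseline MEDAS.
2. **Secondary.** Same model and contrast, each with its own baseline score, Holm-adjusted across four: DASS-21 anxiety, DASS-21 depression, MFIS total, PSQI global.
3. **All else.** Brochure-only contrasts, the 3-month visit, nutritional status, anthropometrics and the remaining scales as estimates with 95% CIs and no significance claim.
4. **Wording.** Change pregnant women to lactating women, and label the determinants regression a secondary observational analysis serving Objective 2.

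MEDAS is proposed because adherence comes first in the aim. The sponsor may prefer another primary outcome or contrast; the aim's wording could also place the brochure-only group among the women who received an intervention. The essential step is to name one outcome, contrast, visit and model in advance. The document is dated May 2026 and does not say whether outcome data have been seen, so the revision should state this.

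Cost: one rewritten section and no new data collection. The downside is that fewer outcomes can carry a significance claim.

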The participants are divided into three groups. The first group receives nutritional education from a qualified nutritionist and a brochure about the Mediterranean diet. The intervention includes the importance and health benefits of MedDiet, mental health, good food sources, and lifestyle practices to maintain good nutritional status and mental health during lactation, with regular reminders about the importance of a healthy diet. These reminders are communicated through channels such as text messages or WhatsApp. The second group receives only the brochure. The brochure includes the definition and components of MedDiet, its health benefits, food sources, food alternatives rich in minerals such as iron, calcium, and B vitamins, and the importance of healthy lifestyles, including increasing physical activity and avoiding smoking. Lastly, the third group is the control group. They do not receive educational interventions or brochures. However, due to ethical considerations, the control group will receive the education and brochure after completing the study.

Statistical analysis

The database will be built in Microsoft Excel, with duplicate entries to verify data consistency. Data processing and analysis will be performed using SPSS 24 (IBM, NY, USA).

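### Depression, anxiety and stress are analysed by name only as four severity classes; no baseline-adjusted comparison of the DASS-21 or BDI scores by arm is specified, and an unordered chi-square on the classes could cost half the power or more

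*Combined protocol and SAP*

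**What the plan says.** The title names anxiety and depression among the outcomes. The Questionnaires section lists the DASS-21 and, separately, the Beck inventory, and both are self-report scales. Follow-up is at 3 and 6 months.

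The Statistical analysis section then does the following.

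- It describes depression, anxiety and stress by the prevalence of their severity.
- It says that Pearson's chi-square "test will be used for categorical data to test for association and probability", and singles out the relation of sociodemographic variables and nutritional status to severity.
- It uses logistic regression for the determinants of severity and then an ordinal model: "For the ordinal regression modeling, the severity is coded as normal = 0, mild = 1, moderate = 2, and severe = 3".
- It lists a Student's t-test between groups, a Shapiro–Wilk check, means with SDs, and correlations for quantitative variables. None of these is tied to a named mental-health score.

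Treatment arm is not named as a term in the chi-square or regression sentences, and adjustment for the baseline score is not mentioned.

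On size, the Sample size section gives a total, "which assumes the number of participants to be 180", reached "considering a 20 % non-response rate in cohorts". Under Educational Intervention, "The participants are divided into three groups"; the allocation ratio is not given.

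**The concern.** Two women with quite different scores count as equal if they fall in the same class, and a one-point change across a cut-off counts as a full step. Pearson's chi-square loses more, because it also ignores the order of the four classes. The loss grows as more women fall in the lowest class.

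The design excludes "lactating women diagnosed with mental diseases". This makes a large normal class plausible, but the plan gives no frequencies.

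At stake is whether a moderate effect on two title outcomes could be detected. If the arms were compared through the classes alone, the trial could report no effect on depression or anxiety while holding scores that would have had a much better chance of showing one.

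**Working it through.** **1. Sample size and number per arm.** The stated basis is "The sample size is calculated using 95 % confidence and an RR of 1.9" with 20% non-response. Power and the reference event rate are not given, so 180 cannot be reproduced uniquely. One route comes close: two arms, reference rate 0.25 (so 1.9 × 0.25 = 0.475), 80% power and no continuity correction need 71 per arm, and 2 × 71 / 0.8 = 177.5, or 178. The same inputs for three arms give 3 × 71 / 0.8 = 266.25, or 267. The total is therefore taken as given.

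If 180 already includes the loss and allocation is equal, 180 × 0.8 / 3 = **48 per arm**. If 180 is the number completing, 180 / 3 = 60 per arm. The plan states neither.

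**2. Other assumptions.** These are a two-sided test at 0.05, one education arm against control, and a true standardised difference of d = 0.5 in favour of education (0.3 to 0.6 also tried). Control class splits (normal/mild/moderate/severe) run from 50/20/20/10 to 80/10/7/3, with even classes as a favourable case. None of the effect sizes or splits comes from the documents.

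**3. Power on the score.** The noncentrality is d × √(n/2) = 0.5 × √24 = 2.449, with 2 × 48 − 2 = 94 degrees of freedom and a critical value of 1.986. The noncentral t gives **68%**. For d = 0.3, 0.4 and 0.6 the same calculation gives 31%, 49% and 83%.

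**4. Power on the classes.** A normal score was simulated in each arm and cut at the control quantiles. The classes were then tested by a 2 × 4 Pearson chi-square (3 degrees of freedom) and by a tie-corrected Wilcoxon test, which stands in for the proportional-odds test. Results at 48 per arm and d = 0.5, with 10,000 runs per row:

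| Control split | Score, t-test | Pearson chi-square | Ordered test | Chi-square / t | Ordered / t |
|---|---|---|---|---|---|
| 25/25/25/25 | 68% | 43% | 61% | 0.63 | 0.90 |
| 50/20/20/10 | 68% | 37% | 53% | 0.54 | 0.79 |
| 60/15/15/10 | 68% | 32% | 49% | 0.47 | 0.72 |
| 70/12/12/6 | 68% | 25% | 43% | 0.37 | 0.63 |
| 80/10/7/3 | 68% | 17% | 33% | 0.25 | 0.49 |

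**5. Sensitivity.**

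- *Effect size:* across d = 0.3 to 0.6, chi-square keeps 0.44–0.53 of the t-test's power at 60/15/15/10 and 0.25–0.28 at 80/10/7/3. The ordered test keeps 0.71–0.76 and 0.49–0.53.
- *Sample size:* at 60 per arm and d = 0.5, the t-test has about 78%. From 50% to 80% normal, chi-square falls from 45% to 22% and the ordered test from about 63% to 41%.
- *Shape:* with skewed scores (t-test power 53–67%), chi-square keeps 33–60% of the t-test's power and the ordered test 68–84%.

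**6. Sparse cells.** With 10% severe, the expected count per arm is 48 × 0.10 = 4.8; with 3% it is 48 × 0.03 = 1.44. With no true difference, chi-square at nominal 5% rejected in 5.1%, 4.9%, 4.8% and 3.7% of runs for the four unequal splits, from 50/20/20/10 to 80/10/7/3.

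**The case against.** The strongest reply is that the plan does not discard the scores. It lists a between-group t-test, means with SDs, a normality check and correlations for quantitative variables, and nothing says that the Beck inventory is cut into classes. A reader might infer that every analysis of mental health is categorical, and the text does not support that. The t-test could be applied to the scores. But the plan does not say so, a t-test compares only two groups while the trial has three, and baseline adjustment is absent. The gap is one of specification.

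A reader might also infer that the treatment effect will be tested by an arm-by-class chi-square. The chi-square sentence stresses sociodemographic variables and nutritional status, and the regression is for determinants of severity. Its general wording for categorical data leaves an arm comparison open, but does not commit to one. The chi-square figures above therefore show what that choice would cost, and do not describe a stated primary test.

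Two further readings go too far. Ordinal regression does not in general halve the power: it uses the order of the classes, and nears half only when about 80% of women are normal. Sparse cells do not make the chi-square invalid here, since its error rate stays at or somewhat below nominal.

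Finally, excluding diagnosed mental illness does not show that most women will score normal, because undiagnosed postpartum symptoms remain possible. This objection stands, and it is why a range of splits is given.

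**Conclusion.** The point holds as a gap in specification with a potentially large cost. The methods attached by name to depression, anxiety and stress work on severity classes, and no baseline-adjusted comparison of the scores by arm is specified for outcomes that stand in the title.

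At 48 per arm and a true 0.5 SD difference, with half to four-fifths of control women in the normal class, a chi-square on the classes keeps roughly a quarter to a half of the power of a t-test on the score. An ordered test keeps roughly a half to four-fifths. Even with evenly filled classes, chi-square keeps only about 0.63.

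The direction of the loss appears in every scenario tried. Its size rests on equal allocation, on how 180 relates to the 20% loss, and on an effect size and class frequencies that the documents do not give. It is a change that should be made, not evidence that the planned tests are invalid.

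**What to change.** - Name the continuous DASS-21 subscale scores and the BDI score as the analysed mental-health outcomes.
- Compare them between arms with adjustment for the baseline score, reporting the difference with a robust or bootstrap confidence interval. This removes the grouping loss, and the baseline adjustment can add precision as a separate gain.
- Keep the four severity classes for descriptive tables, where they help clinical readers.
- Where class is still tested against arm, or against another ordered or two-level variable, replace the unordered Pearson chi-square with a linear-by-linear or proportional-odds test. For the treatment comparison, include arm and baseline in the model.
- State which variables the listed t-test covers.

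The cost is SAP wording and slightly more analysis work. No new data or instruments are needed.
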